7. TRIAL MATERIALS

The electric stimulation device used for TTNS is the Stambil +.

7.1. Trial Product (s)

The Stambil + is a class II medical device that requires a prescription for use. It is a multifunction electrotherapy device currently used at TIRR Memorial Hermann for the purpose of motor and sensory recovery in people with paralysis. It has the ability to provide conventional neuromuscular electric stimulation (NMES), transcutaneous electric nerve stimulation (TENS) and Pulsed Galvanic Stimulation electrotherapy. The device has wide-ranging capability and programmability, with stimulation and wave parameters adjusted for the proposed study purpose. The FDA Approved indications for the Empi Continuum are:

As an NMES device, indications are for the following conditions:

- Retarding or preventing disuse atrophy
- Maintaining or increasing range of motion
- Re-educating muscles
- Relaxation of muscle spasms
- Increasing local blood circulation
- Prevention of venous thrombosis of the calf muscles immediately after surgery

As a TENS device, indications are for the following conditions:

- Symptomatic relief and management of chronic, intractable pain
- Adjunctive treatment for post-surgical and post-trauma acute pain
- Relief of pain associated with arthritis

As a Pulsed Current device, indications are for the following conditions:

- Reduction of edema (under negative electrode)
- Reduction of muscle spasm
- Influencing local blood circulation (under negative electrode)
- Retardation or prevention of disuse atrophy
- Facilitation of voluntary motor function
- Maintenance of increase of range of motion

As a functional electrical stimulation (FES) device, the indications for the following condition:

- Stimulation of the leg and ankle muscles of partially paralyzed patients to provide flexion of the foot, thus improving the patient's gait

7.2. Storage and Drug Accountability

There are no special storage needs for the device. They will be stored in the locked office of the PI in a dry, dedicated place.

8. TREATMENT

8.1. Rationale for Selection of Dose

Neuromodulation of the bladder is currently available with percutaneous TNS in the clinic setting, for a variety of patient populations. Stimulation frequency of 10 Hz and pulse width of 200ms in continuous mode will be used.^{13,14}

Neuromodulation of the bladder has been shown to be effective after 6-8 sessions, with sessions performed once weekly over 12 weeks or 3 times weekly. The 30 minute stimulation session is commonly used for bladder neuromodulation.^{23, 24}

8.2. Study Drug Formulations

NA

8.3. Study Drug Administration

NA

8.4. Specific Restrictions / Requirements

NA

8.5. Blinding

NA

8.6. Concomitant therapy

Medications that may have an effect upon the bladder will be recorded. The medication classes include: 1) bladder medications, 2) anti-spasm medications, 3) anti-depressants/anxiolytics; 4) neuropathic pain medications.

9. SAFETY MEASUREMENTS

9.1. Definitions

An adverse event is any unfavourable and unintended sign, symptom, or disease temporally associated with the use of a medical treatment or procedure that may or may not be considered related to the medical treatment or procedure.

The FDA definition of unanticipated adverse device effect will be used, as followed: *An unanticipated adverse device effect* as defined by FDA regulations at 2CFR 812.3(s) – Any serious adverse effect on health or safety or any life-threatening problem or death caused by, or associated with, a device, if that effect, problem, or death was not previously identified in nature, severity, or degree of incidence in the investigational plan or application (including a supplementary plan or application), or any other unanticipated serious problem associated with a device that relates to the rights, safety, or welfare of subjects.

Skin irritation, inflammation, and electrode burn beneath the electrodes are potential adverse events directly related to the use of electric stimulation.

9.2. Collecting, Recording and Reporting of Adverse Events

The Investigator will be responsible for collecting and reporting adverse events during the UDS. The research assistant and the PI will collect adverse events related to the randomized control trial.

Grading of the severity of the adverse events will be made by the PI, using the Common Terminology Criteria for Adverse Events v4.0 developed by the National Cancer Institute. The relevant “Burn” category is included below.

| DERMATOLOGY/SKIN | | | | | | | Page 1 of 3 |
|------------------|------------|--|---|---|-------------------------------|-------|-------------|
| | | Grade | | | | | |
| Adverse Event | Short Name | 1 | 2 | 3 | 4 | 5 | |
| Burn | Burn | Minimal symptoms; intervention not indicated | Medical intervention; minimal debridement indicated | Moderate to major debridement or reconstruction indicated | Life-threatening consequences | Death | |

REMARK: Burn refers to all burns including radiation, chemical, etc.

Reporting procedures for:

- Deaths and life threatening events
- other SAEs
- Other adverse events

The PI will report problems according to the UTHSC-Houston IRB policy, specifically in the event which in the opinion of the PI is both unexpected and related and places subjects or others at risk of harm.

The PI will report the reportable events to CPHS via iRIS within 7 days, unless the report involves the death of a participant, in which case the report needs to be provided to CPHS within 24 hours.

9.3. Safety Monitoring Plan

The Data Safety Monitoring Plan (DSMP) for the research study includes periodic statistical analysis on rates of morbidity of study participants compared to controls by the PI and the

statistician. Because of the rolling recruitment in the proposed protocol, we anticipate the number of recruited individuals will be sufficient for morbidity review quarterly.

Specifically, we will focus on the occurrence of UTI. We hypothesize that the rate of UTIs in TTNS group will be similar to the SCI population. Based on literature, the overall rate of UTI in SCI is about 2.5 episodes per patient per year. As a result, we expect to see 0.2 episodes per patient during the 4-week study period. Based on that, we construct the stopping rules to stop at 20% UTI rate using lower 90% exact Blyth-Still-Casella confidence bounds. If the number of patients with UTI exceed 3 in the first 5 patients, 4 in the first 10 patients, or 5 in the 14 patients, then patient accrual will be paused pending a review by a medical advisory board comprised of SCI experts.

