4. TRIAL SCHEDULE

Table 2. Timeline of protocol per subject

Weeks in Study Protocol

| Activities | 0 | W1 | W2 | W3 | W4 |
|--|---|---------|----|----|----|
| Clinic Enrolment: | | | | | |
| Eligibility screen | X | | | | |
| Informed Consent | X | | | | |
| Incontinence Questionnaire (I-QOL) | X | | | | |
| Side effect questionnaire | X | | | | |
| TTNS demonstration | X | | | | |
| Home | | | | | |
| Bladder diary | | □-----□ | | | |
| I-QOL | | | X | | X |
| TTNS | | □-----□ | | | |
| Discontinue bladder medication | | | X | | |
| Side effect questionnaire/ TTNS survey | | | | | X |

5. STUDY DESIGN (Table 2)

Anticipated number of patients to screen: 40

- Anticipated number of patient to enrol: 20
- Anticipated drop out or loss to follow-up: 4

Approximate time to complete study recruitment: 1 year

Expected duration of subject participation: 4 weeks

TTNS protocol: (please refer to protocol HSC-MS-15-0806) electrodes 2 inch by 2 inch will be placed according to anatomic landmarks, with the negative electrode behind the internal malleolus and the positive electrode 10cm superior to the negative electrode, verified with rhythmic flexion of the toes secondary to stimulation of the flexor digitorum and hallicus brevis. The intensity level will be set to the amperage immediately under the threshold for motor contraction. If there is not contraction seen, maximal tolerable intensity will be used. In addition, if the patient perceives pain, the intensity will be lowered until comfortable. Stimulation frequency of 10 Hz and pulse width of 200ms in continuous mode will be used.^{13, 14}

- Information gathered:
 - o Clinical demographics, morbidity, and Neurologic Exam findings from interview with subjects, exam, and EMR review.

- Bladder diary will include:
 - use of TTNS with amperage and presence of toe flexion, and pain score 0-10
 - log of catheterization, volumes
 - log of incontinence episodes
 - Description of other observed changes, including but not limited to: fatigue, vision changes, mental status, bowel program changes, and sexual function changes.
- Information will be tabulated on an Excel spreadsheet on my personal work desktop, password protected. Any paper data (bladder diary) will be de-identified and retained in a locked drawer in the locked office of the PI.

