6. METHODS AND ASSESSMENTS

- a. Physical exam will be performed per usual care at TIRR, by the attending SCI physicians. Data will be retrieved from the electronic medical record and placed into the data spreadsheet. Missing data will be requested from the attending physician or directly from the patient.
- b. Transcutaneous Tibial Nerve Stimulation (TTNS) will be placed daily by trained research assistants in the clinic to determine if the subject meets I/E criteria. Skin inspection will be performed before and after the trial stimulation session at the electrode sites.
- c. The Bladder diary will be used to collect data use of TTNS with amperage and presence of toe flexion, pain score 0-10, as well as incontinence episodes and volumes. The research assistant will call weekly to capture the written data and monitor progress with the protocol.

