6.4. Study Visits and Procedures

- *Screening Visits and Procedures*

Screening will be performed in the SCI clinic by the PI and co-I SCI attendings.

Those that meet the I/E criteria will be approached for the study by the PI and co-I attendings. They have until the study period is complete to decide whether they want to participate. However, they will have to return to clinic to have the TTNS trial performed and the directions for home use.

- *Study Visits and Procedures*

Subjects will have their first study visit after their normal clinic visit. Once consented, we will trial TTNS for a response of toe flexion. If they have a response, they will be included in the study. If no response or not tolerating electric stimulation, they will not be included in the study.

Participants will have direction in clinic on the use of the Stambil+, including written, oral, and smartphone images/video if they have access.

The electric stimulation protocol will use stimulation frequency of 10 Hz and pulse width of 200ms in continuous mode for 30 minutes daily, beginning as soon as possible. For sexually active women of child-bearing age, the home use will begin after the results of a pregnancy test are provided. The goal is daily use of TTNS for 4 weeks.

Subjects will be called weekly to capture the information from the bladder diary log and to monitor progress of protocol. They will also be reminded to change electrodes weekly.

- *Final Study Visit:*

Upon completion of the 4-week protocol, subjects will return with the stimulator and the bladder diary.

- *Post Study Follow up and Procedures*

The data will be statistically analysed in the post-study follow up. Subject participation is not required.

- *Discontinuation Visit and Procedures*

If withdrawal occurs, no evaluation will be required for the final study visit, regardless of the withdrawal reason. There are no safety risks in withdrawing from this study at any point.

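### Only a UTI count pauses accrual or calls the advisory board; a severe electrode burn triggers neither, and home skin condition is not a listed item

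*Combined protocol and SAP*

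**What the plan says.** The pause rule appears in sections 2.4b, 9.3 and 11.2 with the same thresholds: "If the number of patients with UTI exceed 3 in the first 5 patients, 4 in the first 10 patients", or 5 in the 14, accrual stops until a medical advisory board of SCI experts has reviewed the data. No other event is tied to a pause or to that board.

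On skin, section 9.1 states: "Skin irritation, inflammation, and electrode burn beneath the electrodes are potential adverse events directly related to the use of electric stimulation". Section 9.2 has the PI grade severity by CTCAE v4.0 and prints the burn row, grades 1 to 5. Reporting to the IRB is specifically for an event that "in the opinion of the PI is both unexpected and related and places subjects or others at risk of harm".

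On ascertainment, section 6 item b says: "Skin inspection will be performed before and after the trial stimulation session at the electrode sites". That is the clinic session used to check eligibility. At home, the stimulation items of the diary (section 5) are "use of TTNS with amperage and presence of toe flexion, and pain score 0-10"; the rest are catheterization and volumes, incontinence, and an open field for other changes whose examples do not include skin. Section 6.4 adds: "Subjects will be called weekly to capture the information from the bladder diary log and to monitor progress of protocol". Intolerance to stimulation is a reason for discontinuation in section 3.5, yet section 6.4 says: "If withdrawal occurs, no evaluation will be required for the final study visit, regardless of the withdrawal reason".

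**The concern.** Safety of home use is part of Primary Objective 1, and section 1 says that the safety of home TTNS is a gap in knowledge. The harm that the plan itself ties to the device is skin injury under the electrodes. UTI is a background event, which the plan expects at the usual SCI rate. The formal stopping rule therefore watches the background event and leaves the device-specific one to discretion.

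Two things are at stake. First, a grade 3 burn would oblige neither a pause nor outside review. IRB reporting may not fill that gap, because burns are listed in advance and the PI could judge one to be expected. Second, the safety result could be incomplete: a subject who stops because of a skin reaction is the one most likely to have something to report, and is also one for whom no evaluation is required.

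**Working it through.** **1. The plan's own rule.** Inputs from section 9.3: 2.5 UTI episodes per patient-year, 4 weeks, a 20% rate, a 90% bound.
- Expected episodes: 2.5 × 4/52 = 0.192, which agrees with the stated 0.2.
- Exceeding 3, 4 and 5 means a pause at 4/5, 5/10 or 6/14. The two-sided 90% Clopper-Pearson lower bounds there are 0.343, 0.222 and 0.206, all above 0.20. One count lower they are 0.189, 0.150 and 0.153, all below. The printed thresholds reproduce on that bound.
- The chance of a pause over the three looks is 5.6% at a true 20% UTI rate and 24.7% at 30%. Skin data do not enter the rule, so no burn rate or grade can trigger it.

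**2. Other routes for a severe burn.**

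| Route | Section | What it does for a burn |
|---|---|---|
| UTI pause and board | 2.4b, 9.3, 11.2 | Nothing |
| Burn grading | 9.2 | Records a grade; no action attached |
| IRB reporting | 9.2 | Only if the PI judges it unexpected, related and a risk of harm |
| Unanticipated device effect | 9.1 | Possible if serious and of unanticipated severity or incidence |
| Quarterly PI and statistician review | 9.3 | Covers morbidity; no threshold; skin not named |
| Lower intensity, hypoallergenic electrode, discontinuation | 2.4b, 3.5 | Help the individual; no escalation |

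**3. What the preliminary data allow.** Section 1 reports no directly related events, with 11 of 12 inpatients complete and 1 ongoing. The one-sided 95% upper limit for zero events is 1 − 0.05^(1/n):
- n = 11: 1 − 0.05^(1/11) = 0.238
- n = 12: 1 − 0.05^(1/12) = 0.221

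So a rate up to 22–24% is not excluded. This is small-sample arithmetic from inpatient use. It shows that the pilot is not strong reassurance; it does not show that burns are likely.

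**4. Cost of a single-event trigger.** Let q be the true proportion of subjects with a device-related skin event of grade 3 or higher. The chance of at least one such subject among n is 1 − (1 − q)^n. The values of q are assumptions.

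| q | n = 14 | n = 20 |
|---|---|---|
| 0.5% | 1 − 0.995^14 = 0.068 | 1 − 0.995^20 = 0.095 |
| 2% | 1 − 0.98^14 = 0.246 | 1 − 0.98^20 = 0.332 |

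Each such pause would follow a real severe event and would last only until the board had reviewed it.

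**5. Whether a count boundary would add much.** With an assumed acceptable rate of 5% for grade 2 or higher and looks at 5, 10 and 14, Clopper-Pearson gives a pause at 2/5, 3/10 or 3/14 (5% tail), or at 2/5, 2/10 or 3/14 (10% tail). At a true 10% rate these cross with probability 0.19 and 0.29. That is weak detection resting on a rate that the documents do not supply.

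**The case against.** The best defence is that skin safety has several layers already, and most of it stands.

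- Intensity is first set just below the motor threshold, a visible endpoint that needs no sensation. The fallback, "If there is not contraction seen, maximal tolerable intensity will be used", applies only when no contraction appears, and subjects without toe or plantar flexion in clinic are excluded. A reader might infer that current is uncontrolled in subjects without leg sensation. The documents do not support that. It is true only that the fallback and the pain rule depend on feeling the current, and that Table 1 does not require leg sensation.
- A reader might infer that home skin events go unrecorded. That also goes too far. Adverse events are collected generally (9.2), the diary's open field is not limited to its examples, there is a week-4 side-effect questionnaire and TTNS survey, and subjects return for a final visit. The response to redness lasting to the next day presupposes that someone reports it. The diary form, questionnaire, survey and case report form are not shown, so a skin question may exist there.
- A reader might infer that a severe burn would go unreported. It might instead qualify as an unanticipated device effect, since burn is listed without an expected severity or rate, and the institution's IRB policy is not shown.
- The plan gives a reason for its focus on UTI, and the device is a class II product in routine use.

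None of this attaches a pause or board review to any burn grade, and waiving evaluation at withdrawal does nothing to secure ascertainment there.

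**Conclusion.** The point holds as a gap in escalation, with a smaller gap in listed ascertainment. As written, no grade of electrode burn obliges a pause or advisory-board review. Skin is not a named item for the home diary or weekly call, and withdrawal for intolerance needs no evaluation. The escalation half rests on sections 9.1 to 9.3 alone and is firm. The ascertainment half would soften if the forms that are not shown carry a skin question.

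No figure in the plan is wrong here, and nothing shows that burns are frequent. This is a low-cost improvement to the measurement of a primary safety objective. The only sizes that can be given, a single-event pause chance of about 7% to 25% over 14 subjects, depend on assumed grade 3 or higher rates of 0.5% to 2%.

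**What to change.** In sections 9.2 and 9.3, add that accrual pauses pending review by the existing medical advisory board on any single device-related burn or electrode-site skin event of grade 3 or higher, whether or not it was expected. Carry the same sentence into 2.4b and 11.2, where the UTI rule is repeated. In section 6.4, add a question about electrode-site skin to the weekly call, and ask it once by phone when a subject withdraws.

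Board referral of grade 2 events is optional. I would not add a count boundary, for the reason shown in step 5 of the working.

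The cost is a short amendment, one question per call and one call per withdrawal, using the same grader, research assistant and board. The downside is the chance of a temporary pause tabulated in step 4.

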2.3. Secondary Objectives

Secondary Objective 1: I-QOL scores will improve and incontinence episodes will reduce after TTNS compared to baseline.

Secondary Objective 2: The frequency of catheterization and the volumes voided will improve with TTNS compared to baseline based on bladder diary.

Secondary Objective 3: Anticholinergic side effects will be reduced based on survey after TTNS protocol.

2.4. Potential Risks and Benefits:

a. End Points - Efficacy

Specific Aim 1: No efficacy requirement for the safety and feasibility studied in specific aim 1.

Specific Aim 2: We expect improved I-QOL scores compared to baseline. As a pilot trial, we have not powered the study for this measure. Results from this study will provide effect size to power a larger study.

b. End Points - Safety

Urinary Tract Infection (UTI) risk:

We expect the rates of morbidity to be the same between those who participate and those who do not. However, because UTI is directly related to the bladder, we will focus on the occurrence of UTI. Based on literature, the overall rate of UTI in SCI is about 2.5 episodes per patient per year. As a result, we expect to see 0.2 episodes per patient during the 4-week study period. Based on that, we construct the stopping rules to stop at 20% UTI rate using lower 90% exact Blyth-Still-Casella confidence bounds. If the number of patients with UTI exceed 3 in the first 5 patients, 4 in the first 10 patients, or 5 in the 14 patients, then patient accrual will be paused pending a review by a medical advisory board comprised of SCI experts.

Bladder medication discontinuation risk:

- Worsened incontinence

Electric Stimulation Risks:

Electric stimulation is commonly performed on the extremities of those with spinal cord injury at the study institution. There are few adverse reactions to electric stimulation. The common ones include:

- Pain with electric stimulation: in these cases, the intensity is reduced until it is comfortable.
- Skin irritation: it is common for redness to occur on the skin at the site of the surface electrode. This typically dissipates within an hour of removing the electrode. In some cases, the redness remains the next day. In these cases, they are likely sensitive to the adhesive used and a hypoallergenic skin electrode will be provided.

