3.6. Subject Replacement

Subjects who drop out will be replaced by recruitment from the SCI clinic and asking for informed consent from those who meet the I/E criteria.

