11. SAMPLE SIZE AND STATISTICAL METHODS

11.1. Determination of Sample Size

For SA 1, safety, feasibility, compliance, we use as a convenient sample size. The preliminary data with 12 subjects have shown high compliance, lack of adverse events, and feasibility. So we believe 14 is sufficient and we will enrol 20 patients to account for non-compliance in the outpatient setting. This study will help us to determine effect size for future studies.

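### The UTI pause rule has no boundary after patient 14 although 20 patients are to be enrolled, so up to 6 planned patients have no numeric trigger for board review.

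*Combined protocol and SAP*

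**What the plan says.** - **The rule.** Sections 2.4 b, 9.3 and 11.2 print the same rule. The method is "we construct the stopping rules to stop at 20% UTI rate using lower 90% exact Blyth-Still-Casella confidence bounds". The trigger is that the number of patients with UTI should "exceed 3 in the first 5 patients, 4 in the first 10 patients, or 5 in the 14 patients", and the consequence is "then patient accrual will be paused pending a review by a medical advisory board comprised of SCI experts". The last look runs straight into that consequence, "or 5 in the 14 patients, then patient accrual will be paused pending a review", and no further look follows.
- **Enrolment.** Section 11.1 states "So we believe 14 is sufficient and we will enrol 20 patients to account for non-compliance in the outpatient setting". Section 5 also gives 20 to enrol, with 4 expected to drop out or be lost.
- **Replacement.** Section 3.6 states "Subjects who drop out will be replaced by recruitment from the SCI clinic", with no cap.
- **Other monitoring.** Section 9.3 plans a quarterly review of morbidity by the investigator and the statistician, with attention to UTI. It gives no count or rate that calls for action, and it refers to a comparison with controls, which this single-arm study does not have.

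**The concern.** The first two looks are at the first 5 and the first 10 patients. The last is at the 14 patients, as if 14 were the whole study. That is the number section 11.1 calls sufficient, not the number to be treated.

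Safety is part of Primary Objective 1, and UTI is the only safety event with a numeric rule. If the rule is followed as written, a count that is borderline at patient 14, or an excess that appears later, meets no boundary that sends the question to the board. Six of 20 patients (30% of planned enrolment) fall outside it.

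**Working it through.** **1. Reference rate.** Section 9.3 says that "the overall rate of UTI in SCI is about 2.5 episodes per patient per year". Over 4 weeks this is 2.5 × 4/52 = 0.19, which agrees with the plan's 0.2 and its 20% limit.

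**2. Reproducing the printed counts.** For x patients with UTI among n, the one-sided 5% exact (Clopper-Pearson) lower bound is above 20% when P(X ≥ x | n, 0.20) < 0.05. This is the lower end of a two-sided 90% interval.

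| n | Count that does not trigger: tail at 20% (lower bound) | Count that triggers: tail at 20% (lower bound) | Implied rule |
|---|---|---|---|
| 5 | 3: 5.8% (0.189) | 4: 0.7% (0.343) | more than 3 |
| 10 | 4: 12.1% (0.150) | 5: 3.3% (0.222) | more than 4 |
| 14 | 5: 13.0% (0.153) | 6: 4.4% (0.206) | more than 5 |
| 20 | 7: 8.7% (0.177) | 8: 3.2% (0.217) | more than 7 |

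The first three rows are the printed rule exactly. The fourth extends it to 20.

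**3. The named method.** A Blyth-Still-Casella calculation does not fit the printed wording at all three looks.
- Two-sided 90%: the lower bound first passes 20% at 3/5 (0.247), 5/10 (0.249), 6/14 (0.224) and 7/20 (0.202). The looks at 10 and 14 match. The look at 5 does not, because 3 of 5 would already trigger. At 20 this reading gives more than 6.
- One-sided 90% (two-sided 80%): the bound first passes 20% at 3/5 (0.318), 4/10 (0.209), 5/14 (0.216) and 7/20 (0.232). The printed numbers 3, 4 and 5 would then be counts to reach, not to exceed.

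**4. Patients without a boundary.** All enrolled: 20 − 14 = 6. Expected completers only: (20 − 4) − 14 = 2.

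**5. Chance of a pause.** Assume independent patients with a common UTI probability p. Let f(n, k) be the probability of k patients with UTI among n with no pause so far. Then f(n, k) = f(n−1, k)(1 − p) + f(n−1, k−1)p, and states above the boundary are removed at each look. The added boundary is more than 7, checked at each of patients 15 to 20.

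| True rate | Printed rule | Added boundary, through patient 20 | Added boundary, crossings by patient 19 only |
|---|---|---|---|
| 20% | 5.6% | 6.7% | 6.2% |
| 30% | 24.7% | 30.9% | 28.2% |
| 40% | 54.3% | 65.6% | 61.4% |
| 50% | 80.5% | 89.8% | 87.0% |

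The last column matters because the rule only pauses accrual, and a crossing on patient 20 leaves no planned accrual to pause.

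**6. Ending high without a pause.** Under the printed rule, the chance of finishing with at least 8 of 20 and no pause is 1.1%, 6.2%, 11.3% and 9.3% at true rates of 20%, 30%, 40% and 50%.

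**The case against.** **The 14 may be the evaluable set, and the 20 may already include replacements.** This is possible, since section 11.1 explains the 20 as an allowance for non-compliance. It narrows the gap but does not close it: 20 less 4 expected losses is 16, and nothing limits the UTI count to completers. It does mean that 6 is an upper figure for planned enrolment, and that exposure beyond 20 is not established.

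**Later patients are still watched.** True: the quarterly review covers them, section 9.2 sends unexpected and related problems to the IRB, and nothing bars a referral to the board. A reader might infer that a late excess cannot reach the board, but the documents do not say so. What is missing is a number that requires it.

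**The gain is modest and depends on timing.** This stands. UTIs are counted over 4 weeks with rolling recruitment, so reports will lag. If only crossings by patient 18 count, the pause chance is 26%, 58% and 84% at true rates of 30%, 40% and 50%; by patient 17 it is 25%, 55% and 82%, almost no gain over the printed rule.

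**Two stronger readings are tempting.**
- A reader might infer that 11 of 20 patients could have a UTI unnoticed. The arithmetic is right (5 + 6 = 11), but this needs exactly 5 of 14 followed by 6 of 6. Its probability is 0.0005% at a true 20% rate and still only 0.17% at 50%.
- A reader might take more than 6 as the boundary at 20, which would raise the pause chance to 42%, 77% and 95%. Its tail at a 20% rate is 8.7%, looser than every printed look (0.7%, 3.3%, 4.4%), and the reading that yields it does not reproduce the printed count at 5. Part of that larger gain comes from a looser criterion, not from closing the gap.

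**Conclusion.** The point holds in limited form. The plan's only numeric safety rule stops at 14 patients in a study that enrols 20, leaving 2 to 6 planned patients without a trigger. Extended at the level that reproduces the printed counts, the rule gains about 6, 11 and 9 percentage points of pause probability at true rates of 30%, 40% and 50%, or about 4, 7 and 7 points if only crossings by patient 19 count. These figures assume independent patients, a common UTI rate, the literal reading of exceed, and UTIs known when the count is checked; reporting lag would reduce them. The gap itself does not depend on which confidence-bound reading was intended. The 11 of 20 outcome is a literal worst case and says little about practical risk.

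**What to change.** Make the same changes in sections 2.4 b, 9.3 and 11.2:

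1. State that the rule counts every patient who starts home stimulation, including dropouts and replacements.
2. Reconcile the wording of the last look with the enrolment of 20, so that 14 is described as the first 14 patients.
3. Add a boundary after patient 14, derived by the same method and level as the printed counts and checked as each UTI is reported, so that it can act while accrual remains. The one-sided 5% exact reading gives more than 7 by 20 patients.
4. Before fixing the number, confirm it with the named Blyth-Still-Casella method. State whether the 90% is one-sided or two-sided and whether the printed counts are to be reached or exceeded.

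The cost is one added boundary in three identical paragraphs, and a rise in false pauses at a true 20% rate from 5.6% to 6.7%. A false pause leads to a review of accrual. Sample size, visits and study treatment are unchanged.
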